It is impossible to predict which infants will be non-vigorous prior to delivery and it is anticipated that about 3 percent of deliveries will be non-vigorous. It is also stressful for expectant parents to be approached for a study where it would be unlikely that their child would be non-vigorous at birth. In addition it would be unethical to add additional time for individual patients to be randomized at birth where a rapid decision for cord management would be needed. Therefore, we are proposing a cluster crossover randomized controlled trial where all sites would perform one method of cord management for one year and then cross over to the other approach. This study involves comparing 2 approaches to treatment that are currently in widespread use. We will be comparing outcomes of current practice variation applied with a standardized approach. All infants that were non-vigorous for each study year would be included in the study with collection of a minimal de-identified data set similar to a delivery room registry. The majority of these deliveries are emergent/urgent so we are requesting a waiver of antenatal consent in order to perform this cluster randomized cross-over trial. Parents will be able to opt out prior to delivery by review of handouts, fliers and post-delivery when approach to collect long term follow-up data. The parents will be consented after delivery for permission to collect ongoing information about their infant.

This trial will involve 1200 term newborns needing resuscitation at birth at ten (10) hospitals in San Diego, CA; La Mesa, CA; Loma Linda, CA; Sacramento, CA; Washington, DC; Portland OR; Salt Lake City UT; Edmonton, Alberta, Halifax, Nova Scotia, and Poznan, Poland. This trial will provide evidence to promote a change in guidelines supporting the use of UCM – a simple, no-cost intervention as standard of care in term and near-term newborns needing resuscitation.

II. BACKGROUND AND SIGNIFICANCE

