The primary endpoint to be used for efficacy evaluation is the rate of NICU admission (by predefined criteria). The primary hypothesis to be tested is whether the UCM group's results show a lower event rate compared to the ECC group. The primary analysis will estimate relative risks and 95% confidence intervals, accounting for the cluster randomized crossover study design, with fixed or random effects for treatment group effect, period effect, cluster effect and cluster by period interaction effect. The analysis will also account for multiple gestations and clustering within a pregnancy if more than one neonate of a multi-gestation pregnancy meets eligibility. If the treatment groups are found to differ on a pre-treatment factor known to be a risk factor for the outcome, the statistical analysis will adjust for these differences. An evaluation of treatment by site interaction will be included. The percent of patients missing information to define the primary outcome is expected to near 0%. Death is not an anticipated competing risk for the primary outcome as it is expected that all randomized newborns requiring NICU admission will be admitted immediately. However, a sensitivity analysis will be conducted using a composite outcome of NICU admission (by predefined criteria) or death.

Subgroup analyses should be pre-specified and interpreted with care. Prior studies offer no basis for assuming a priori interactions between treatment groups, strata and subgroups defined by sex, race/ethnicity, gestational age, site or a combination of these groups, beyond that already controlled for in the randomization. For these reasons, preplanned tests for interactions with treatment assignment are not warranted and are not powered for with the sample size. However, in accordance with NIH guidelines, an evaluation of consistency across racial/ethnic subgroups will be included.

Analysis of Secondary Outcomes

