This protocol will not adversely affect the rights and welfare of subjects, and will involve no more than minimal risk to subjects. We will be comparing the outcomes of two current practice variations with a standardized protocol. Based on the current literature to date there are no known risks with early cord clamping or umbilical cord milking in near term and term non-vigorous infants. If the subject is non-vigorous they would receive the assigned standard of care for that year. All subsequent medical care would remain per hospital protocol in both years of enrollment. The only difference would be the standardization of cord management for the year in non-vigorous infants. If parents were to ask if anything would have been different if their baby was not in the study the answer would be no because subjects who are enrolled in the study will receive the same cord management that they would have received if they were not enrolled. The study design requires each delivering hospital to adopt one standard of care for each year of enrollment. However, this may have been a different

cord management than they would have received had the delivering hospital not elected to participate in this study or if the practitioner chose a different cord management based on the clinical situation. Therefore, the permission is to collect ongoing and follow-up data. The majority of these deliveries are emergent/urgent so we are requesting a waiver of consent. This allows the provider and/or research staff to carefully review the study intervention and data collection with the parents after the initial anxiety of an urgent delivery has decreased. We believe this is the correct approach for this trial. Requiring antenatal consent would also adversely affect the generalizability of the data obtained. Without the waiver of consent sites would require antenatal consent and this has been shown to limit the enrollment of the sickest infants in studies by eliminating the ability to obtain consent from mothers with limited prenatal care and/or emergent deliveries. This results in excluding some of the sickest infants that could potentially benefit the most from a trial intervention in which there are minimal risks.

Parents will be notified about the study with the ability to opt out of the trial prior to delivery by the following: 1)

Expectant mothers will receive a brochure and discuss the study with the obstetrical provider at the prenatal visits.

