2) Brochures will be included in the hospital admission packets 3) Posters and signs will be displayed at admission

areas. Every effort to notify all expectant families will be made prior to delivery. While routine practice will be to perform the assigned intervention for that year. A family that opts out can discuss with the clinical team whether they have a different preference for cord management other than the routine practice in the event resuscitation is needed. However, umbilical cord management is ultimately at the discretion of the practitioner based on the clinical situation. If families opt out of the study, the research team will track them on the screening log and the electronic chart may be flagged to not approach the families for consent and ongoing data collection. Each site's PI will be responsible for training their research team members on this process to ensure that no families are approached for ongoing data collection.

Waiver of HIPAA Authorization

Partial waiver of HIPAA Authorization is requested for screening. The use or disclosure will not adversely affect the rights and welfare of the subjects. This research protocol cannot be conducted without partial waiver because investigators would be unable to identify eligible subjects. This will involve no more than minimal risk to the privacy of subjects. Only research investigators/assistants will access PHI for eligibility and screening purposes. The site specific screening log will include: names of subjects, date of birth, medical record number, eligibility based on cord management, admitted to NICU, date consented, reason not enrolled. For all eligible infants, parents will be approached for informed consent and HIPAA authorization.

A full waiver of individual HIPAA authorization is requested for instances when the research team is unavailable to obtain consent (i.e. infant is born and dies or is discharged before study team could approach). This will allow us to collect minimal data that is coded to protect subject's confidentiality. This will support outcome data for the primary outcome. The minimal data collected under waiver will be collected from the existing medical records and will include: information from the delivery room record, admission to NICU, and information from the study source document (appendix 3). We have an adequate plan to protect the identifiers from improper use and disclosure.

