REDCap (Research Electronic Data Capture). All case report forms for the trial will be captured using a secure web-based data capture system REDCap. REDCap under the direction of the UCSD ACTRI Biomedical Informatics division offers and manages REDCap. The ACTRI Biomedical Informatics team will maintain and provide full administration and support for REDCap. Data captured electronically in the delivery room will be uploaded to REDCap for future analysis for all sites. The REDCap application supports many data collection and analysis projects. Data collection projects rely on a thorough study-specific data dictionary defined in an iterative self-documenting process by all members of the research team with planning and analytic assistance from biostatisticians. The iterative development and testing process results in a well-planned data collection strategy for individual studies. The REDCap system provides secure, web-based applications that are flexible enough to be used for a variety of types of research, provide an intuitive interface for users to enter data and have real time validation rules (with automated data type and range checks) at the time of entry. The system has been deployed using a highly secure, HIPAA-compliant network design and is housed in a physically secure data center. Back up of data is performed nightly and archived off-site for two years for Disaster Recovery purposes. Principal investigators may opt to archive the data for up to seven (7) years offsite to AWS Glacier.

Data that will be accessed, used and collected will be identifiable on research-related forms by a study number. We will take the following precautions to maintain the confidentiality of identifiable subject information. We will also keep subject's identity separate from their data on a Master log and coded.

1. Paper-based records will be kept in a secure location and accessible only to persons involved in the study
2. Computer-based files will be available only to persons involved in the study through the use of access privileges and passwords.
3. Prior to accessing any PHI, personnel will be required to sign statements agreeing to protect the security and confidentiality of identifiable health information
4. Whenever feasible, identifiers will be removed from study-related information

Data Collection

Under waiver of individual HIPAA, we will collect the following minimal data set from all eligible subjects (parents that opt out will not be included):

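### The plan leaves unclear whether refusal after delivery removes an infant's primary-outcome data, and no primary analysis covers that loss if it does

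*Combined protocol and SAP*

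**What the plan says.** All references are to the combined protocol and SAP.

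- **Data Collection (section IX).** The minimal data set is collected under waiver from eligible subjects, but "parents that opt out will not be included". No limit is set on when the opt-out occurs. NICU disposition is one of the items.
- **Abstract (section I).** "Parents will be able to opt out prior to delivery by review of handouts, fliers and post-delivery when approach to collect long term follow-up data". That same paragraph says "All infants that were non-vigorous for each study year would be included in the study with collection of a minimal de-identified data set".
- **Waiver of Consent (section VII).** "Parents will be notified about the study with the ability to opt out of the trial prior to delivery by the following", followed by brochures, admission packets and posters. The permission sought after delivery is described as covering ongoing and follow-up data.
- **Waiver of HIPAA Authorization (section VII).** Parents of all eligible infants are approached for consent and authorization. The full waiver is requested "for instances when the research team is unavailable to obtain consent"; the examples are death or discharge before the approach. Refusal after an approach is not mentioned.
- **Statistics (section V).** Analyses are by intention to treat on everyone randomized. For the primary outcome, "The percent of patients missing information to define the primary outcome is expected to near 0" per cent. The only sensitivity analysis named for it is the composite with death. Comparison of those with and without missing data, and multiple imputation, are planned for secondary outcomes.
- **Maintaining Adherence (section IV).** Only pre-defined exclusion criteria remove an infant from the primary analyses, with a check for differential occurrence by treatment. Opting out is not among the criteria in section VI.

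**The concern.** A family that declines when approached has an infant who has already received the assigned cord management and who may already have been admitted. If that refusal deletes the disposition item, the exclusion comes after treatment and may depend on the outcome.

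Section IV says parents cannot be blinded, and the two arms run at different times within each site. Both the approach and the response to it could therefore differ between epochs. Randomization of the order does not protect against selection that operates after treatment. At stake are the intention-to-treat claim and, if refusal depends on admission differently in the two arms, the relative risk itself.

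**Working it through.** **1. What the sections imply together.** The Abstract uses the term opt out for the post-delivery choice. Data Collection drops opt-outs from the minimal set without a time limit. The HIPAA section does not extend the full waiver to families who were approached and declined. On these three sections, a post-delivery refusal removes the primary outcome.

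The Abstract's statement that all non-vigorous infants are included, the Eligibility section's description of the approach as concerning the remaining part of the study, the Waiver of Consent section, and Appendix 1's list of waiver items for all eligible infants point the other way. The text does not settle which applies.

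**2. The plan's own sample size.** Inputs from section V: 25% v 16.25%, two-sided alpha 0.05, power 85%, rho = eta = 0.02, a correction of 4 x cluster size, and 1200 infants at ten sites. Equal site-periods are assumed, so m = 1200/(10 x 2) = 60.

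- Unpooled n per arm = (1.960 + 1.036)² x (0.25 x 0.75 + 0.1625 x 0.8375) / 0.0875² = 379.5.
- Design effect = 1 + (60 - 1) x 0.02 - 60 x 0.02 = 0.98.
- Per arm = 379.5 x 0.98 + 4 x 60 = 611.9, so the total is 1224, within 3% of 1200.
- Power at 600 per arm is 83.6%.

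The figure reproduces, and it contains no allowance for opt-outs in the primary outcome. If opt-outs came out of the 1200, power would be 81.7% at 5% and 79.5% at 10%. Precision is therefore not the main issue.

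**3. Worst-case bounds at the planned rates.** The missing fraction d per arm is assumed, because the documents give no refusal rate. Observed rates among the remainder are taken as 16.25% and 25%.

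- Against UCM: UCM = 0.1625(1 - d) + d; ECC = 0.25(1 - d).
- In favour of UCM: UCM = 0.1625(1 - d); ECC = 0.25(1 - d) + d.

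| d per arm | Against UCM (UCM / ECC) | RR | In favour (UCM / ECC) | RR |
|---|---|---|---|---|
| 1% | 17.1% / 24.8% | 0.69 | 16.1% / 25.8% | 0.62 |
| 2% | 17.9% / 24.5% | 0.73 | 15.9% / 26.5% | 0.60 |
| 5% | 20.4% / 23.8% | 0.86 | 15.4% / 28.8% | 0.54 |
| 10% | 24.6% / 22.5% | 1.09 | 14.6% / 32.5% | 0.45 |

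In the case against UCM, the difference vanishes when 0.1625(1 - d) + d = 0.25(1 - d), so d = 0.0875/1.0875, or about 8%. With an effective (600 - 240)/0.98 = 367 per arm, z falls from 1.99 at d = 2.5% to 1.81 at 3%. Nominal significance is therefore lost at about 3%.

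**4. Illustration of selection.** Take a true rate of 25% in both arms and no differential refusal in ECC. In UCM, assume refusal of 10% for admitted infants and 2% for the others. Observed UCM rate = 0.25 x 0.90 / (0.25 x 0.90 + 0.75 x 0.98) = 0.225/0.960 = 23.4%, and RR = 0.94. With 20% and 5%, it is 0.200/0.9125 = 21.9%, and RR = 0.88. If refusal follows the same pattern in both arms, the observed rates are equal and the RR stays at 1.

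**The case against.** The strongest reply is that no sentence says an approached family that declines loses its minimal data. The Abstract ties the post-delivery choice to long-term follow-up. The Waiver of Consent section places opting out of the trial before delivery. The same section has opt-out families flagged so that they are not approached, which makes opting out and declining consent separate events. Appendix 1 separates waiver items from items collected after consent and puts disposition among the former. On that reading, the parenthesis in Data Collection covers only pre-delivery opt-outs, and the near-zero expectation is reasonable.

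Much of this stands, and it rules out several inferences a reader might draw:

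- That refusing families are definitely dropped. The sections conflict.
- That the near-zero statement is a statistical error. It is an expectation, no figure in the documents contradicts it, and it may refer only to infants already in the data set.
- That every opt-out is a post-treatment exclusion. Pre-delivery opt-outs come before treatment and outcome, although they may come after the site's allocation is known.
- That a particular bias is to be expected. An RR of 0.84 under a true null, for example, needs refusal of 10% (admitted) and 20% (not admitted) in ECC with the reverse in UCM. The documents give no reason to expect opposite patterns.

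What survives the reply is that the Abstract does use the term opt out for the post-delivery choice, the full waiver as worded does not reach families who decline, and no missing-data analysis is specified for the primary outcome.

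**Conclusion.** The plan needs a clarification and would gain from one inexpensive analysis. As written, it permits the reading that a post-delivery refusal deletes the primary outcome. If that reading is the intended one, the analysed set is not the full randomized cohort, opting out is not an exclusion the protocol allows, and neither the near-zero expectation nor the composite with death addresses the loss.

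The size is unknown. It is trivial if refusals are rare or similar in both arms. At an assumed 5% missing per arm, the extreme bounds still favour UCM; at 10% they include no effect. These are extremes at the planned event rates, not predictions. The sample-size calculation is not in question here.

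**What to change.** 1. Reconcile the Abstract, Waiver of Consent, Waiver of HIPAA Authorization and Data Collection sections on whether a post-delivery opt-out removes the minimal data.
2. In the primary analysis section, make the near-zero expectation apply only to infants whose families did not opt out.
3. From the screening log, report eligible infants, pre-delivery opt-outs and post-delivery opt-outs by arm and site-period.
4. If post-delivery opt-outs lose outcome data, pre-specify a best/worst-case or tipping-point analysis of NICU admission that uses only their counts.

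The cost is SAP wording and a tabulation. The log already tracks opt-outs and the reason for non-enrolment. It may need one more item, whether the opt-out came before or after delivery, since that is not among the fields listed. No refused infant-level data are used. The drawback is that the bounds will be wide if refusals turn out to be common; if they are rare, the table supports the intention-to-treat claim.

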Sample size and power calculation We estimated that a sample size of 1200 across ten sites would be needed to test efficacy of UMC versus ECC for the primary outcome. This was based on the following assumptions: a clinically meaningful 35% reduction in NICU admissions (16.25% for UCM versus 25% for ECC), a two-sided type I error alpha = 0.05, 85% power, 0.02 rho (within cluster within period correlation), 0.02 eta (within cluster between period correlation), and a correction factor (4 x cluster size) for the small number of clusters(51).

For the longer-term neurodevelopment outcome scores, we estimated that a sample size of 1200 across ten sites, with an assumed two-sided type I error alpha = 0.05, 0.02 rho, 0.02 eta, a correction factor (4 x cluster size) for the small number of clusters, and Cohen's d = 0.25, power ranges from 79% to 87% when assuming a range in lost to follow-up from 20% to 10%. The original sample size for this trial was 1000. However, at the first DSMB meeting in May 2019 only four sites had begun enrollment and enrollment was nearing completion of the crossover point (nearly 2/3 complete in the first arm), and two sites were unable to obtain IRB approval. Therefore in conjunction with the DSMB, the decision was made to reassess the sample size calculation for ten sites.

Feasibility Based on the numbers of newborns at each of ten sites, we expect a total of approximately 1500 newborns with a 1-minute Apgar of ≤ 3 per year. Estimating conservatively that at least 50% will be classified as non-vigorous, a 2-year period of recruitment would be required. The ten sites agree to recruit and each one has provided an estimated number 35-41+6 weeks infants delivered per year.

Statistical Approaches for Testing Hypotheses

All statistical analyses will be based upon the total cohort of patients randomized into the trial. Patients will be included in the treatment group to which they were randomly assigned. We will use the intent-to-treat analysis to determine treatment difference between the UCM and ECC groups.

Descriptive statistics (counts and proportions for categorical variables and means and standard deviations or medians and interquartile ranges for continuous outcomes) will be used to compare baseline demographic, physiologic and clinical

outcomes between the two treatment groups. All statistical tests are two-sided with alpha = 0.05.

Analysis of Primary Outcome (NICU Admission)

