Secondary outcomes (use of therapeutic hypothermia, use of volume expanders, hemoglobin, bilirubin, death, and neurodevelopmental follow up scores) will be analyzed using similar multivariable procedures accounting for the study design as for the primary outcome to test treatment effects. Analyses will estimate relative risks and 95% confidence intervals for binary outcomes and means or mean differences and 95% confidence intervals for continuous outcomes. Secondary outcomes will be evaluated for missing data and those with and without missing data will be compared. Multiple imputation analysis will be conducted as warranted. Analyses will also evaluate death as a competing risk. No adjustment for multiple comparisons of secondary outcomes is planned.

Exploratory Analyses

Several outcomes are identified as exploratory (level of HIE, blood pressure, length of hospitalization, resuscitation interventions, and placental pathology). These analyses will focus on descriptive statistics rather than hypothesis testing. Likewise any evaluations of subgroup differences by treatment group (other than race/ethnicity as mentioned previously) will be explored in secondary analyses for descriptive purposes and solely for purposes of generating hypotheses for future studies.

Follow up Study- While all secondary and exploratory outcomes that occur during the delivery hospitalization will be presented in the primary paper, all subjects will continue to be followed until 24 months of age to determine their long-term outcome. The sample size is powered to detect differences in their Ages and Stages Composite and MCHAT scores.

Substudies for cerebral oxygenation and echocardiography will be reported as separate projects on clinical trials.gov and analyzed independently.

VI. Recruitment

Eligibility criteria

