Screening ID, Month/Year of birth, gestational age, SGA, time of cord clamping, Breathing or crying prior to cord clamping, birth assessment of tone, number of times cord milked, location of infant when milked (i.e. mothers abdomen, below level of introitus) birth weight, gender, APGARS at 1 and 5 minutes, resuscitation procedures (CPAP, PPV, intubation, chest

compressions, epinephrine, max FiO₂), NIRS data, disposition (NICU admission, or stable and staying with parent), pregnancy and delivery risk factors (diabetes, suspected or confirmed Triple I, hypertension, rupture of membranes).

After Informed Consent we will collect the following full data set:

Maternal data from infant's chart: Age, Race/Ethnicity, Level of Education, Mode of Delivery, Anesthesia (general, Spinal Epidural), Medications, Placental Weight. All maternal data will be collected from the infant's chart; the mother's chart will not be accessed for study purposes.

Infant data: Includes all data collected under waiver, plus Race/Ethnicity, Multiple gestation, length (cm), head circumference (cm), Hemoglobin between 12-48 hrs, Venous and/or arterial cord pH (if available), cardiac US, Peak total serum bilirubin (mg/dL) or Transcutaneous Bilirubin level, Polycythemia in the first week of life (Hct >65%), Duration of phototherapy days, Use of cardiac inotropes (dopamine, dobutamine, epinephrine), Early onset sepsis (positive blood or CSF culture at < 72 HOL), Duration of intubated and mechanical ventilation (days), Need for blood transfusion (DOL of 1st transfusion and total number), Length of hospitalization (total days), ASQ3, MCHAT, MRI white matter injury, HIE: mild, moderate, severe (initial screen completed at 1-6 hours of life), HIE: mild, moderate, severe (highest stage before discharge), Therapeutic Hypothermia, Placental pathology, PPHN.

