Appendix 1 Data Collected**DATA COLLECTED ABOUT INFANTS
AND MOTHERS****Maternal data from infant's chart:**

1. Age
2. Race/Ethnicity
3. Diabetes (gestational, Type 1 or 2) (yes/no)
4. Suspected or confirmed Triple I, chorioamnionitis (yes/no)
5. Hypertension (yes/no)
6. Rupture of Membranes (hours)
7. Mode of Delivery
8. Type of Anesthesia
9. Maternal medications (i.e. magnesium, fentanyl)
10. Placental Weight
11. Level of education
12. COVID-19 confirmed positive

**Data collected from all eligible infants
under waiver:**

13. Screening ID
14. Month/Year of birth
15. Birth assessment of tone
16. ECC or # times Milked
17. Timing of cord clamping
18. Breathing/Crying before cord clamped
19. 1 and 5 min Apgar
20. Resuscitation interventions (cpap, ppv, intubation, compressions, epinephrine, max Fio2)
21. NIRS, HR, SpO2 in del room
22. Gestational Age
23. Birth Weight
24. Gender
25. Disposition(NICU, Death or Dyad care)
26. Infant/delivery risk factors
27. NICU admission Dx
28. Reason Peds called to delivery
29. Multiple Gestation
30. COVID-19 confirmed positive

Infant data collected after consent:

31. Length, FOC (cm)

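### Most secondary outcomes are collected only after post-treatment parental consent, so the total-cohort analysis promised for every outcome cannot be delivered for them

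*Combined protocol and SAP*

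**What the plan says.** Section V (Statistical Approaches for Testing Hypotheses) states: "All statistical analyses will be based upon the total cohort of patients randomized into the trial". It then commits to intention to treat. Analysis of Secondary Outcomes lists what will be tested: "Secondary outcomes (use of therapeutic hypothermia, use of volume expanders, hemoglobin, bilirubin, death, and neurodevelopmental follow up scores".

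Section IX (Data Collection) sets up two tiers of data. Under waiver, "we will collect the following minimal data set from all eligible subjects (parents that opt out will not be included". That set covers delivery-room, resuscitation and disposition data. The second tier is introduced by "After Informed Consent we will collect the following full data set". Appendix 1 repeats the split under "Infant data collected after consent" and places "Disposition(NICU, Death or Dyad care" in the waiver tier.

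Section VI (Eligibility criteria) has parents approached after delivery and resuscitation. Section VII (Waiver of HIPAA Authorization) allows minimal data when consent cannot be obtained, for example when the "infant is born and dies or is discharged before study team could approach".

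For missing secondary outcomes, Section V compares infants with and without data and adds: "Multiple imputation analysis will be conducted as warranted". No section gives an expected rate of post-delivery consent, an analysis set for consented infants, or a plan to report consent by arm.

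**The concern.** Consent here comes after treatment, so having outcome data may depend on how the infant fared and on who was asking and deciding. Section IV (Prevention of Bias) accepts that parents and obstetrical providers cannot be blinded. Each site is told its arm and applies it to every non-vigorous infant for that period, so site research staff can know it too. The plan's own examples of families not reached, infants who die and infants who go home early, lie at opposite ends of severity. Data missing completely at random is therefore not a safe default.

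At stake is the comparability of the arms for the tested secondary outcomes. If the consented subset differs between arms in severity, the estimated effect is no longer protected by the allocation. Whether and how to adjust would be decided after the data are seen.

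**Working it through.** **Step 1. Where each tested secondary outcome is collected.**

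| Outcome (Section V) | Tier | Place |
|---|---|---|
| Therapeutic hypothermia | after consent | Section IX; Appendix 1 item 44 |
| Volume expanders | after consent | Appendix 1 item 37 (volume bolus) |
| Hemoglobin | after consent | Section IX; item 38 |
| Bilirubin | after consent | Section IX; item 40 |
| ASQ-3 / M-CHAT-R | after consent | Section IX; items 60 and 61 |
| Death | waiver, as disposition | item 25 |

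Five of six groups depend on consent. NICU disposition, NICU admission diagnosis (item 27) and resuscitation interventions (item 20) are in the waiver tier.

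**Step 2. The plan's own figure that touches on loss.** Section V gives neurodevelopmental power of 79% to 87% at 20% to 10% loss (d = 0.25, rho = eta = 0.02, 600 per arm, ten sites, so 60 per cluster-period). Take the design effect as 1 + 59(0.02) − 60(0.02) = 0.98, and the small-cluster correction as 4 × 60 = 240 per arm.

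- 10% loss: (540 − 240)/0.98 = 306 effective per arm, power 87.1%.
- 20% loss: (480 − 240)/0.98 = 245 effective per arm, power 79.0%.

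The stated figures are reproduced and are not in error. They allow for how many infants are lost, not for which ones. They hold only if non-consent falls inside the 10% to 20%, which the plan does not say.

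**Step 3. Illustration of bias for hypothermia.** From the plan: NICU admission p = 16.25% (UCM) and 25% (ECC). Assumed, because the documents give no figures: hypothermia in 20% of admitted infants and in no others; consent c_A if admitted and c_N if not.

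True risks: 0.2 × 0.1625 = 3.25% and 0.2 × 0.25 = 5.0%, so RR = 0.65.

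Observed risk among consenters = 0.2·p·c_A / [p·c_A + (1 − p)·c_N].

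Worked case, c_A = 90% and c_N = 60% in both arms:

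- UCM: 0.2 × 0.14625 / (0.14625 + 0.5025) = 4.5%
- ECC: 0.2 × 0.225 / (0.225 + 0.45) = 6.7%
- RR = 0.68

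| c_A (both arms) | c_N UCM | c_N ECC | UCM risk | ECC risk | RR |
|---|---|---|---|---|---|
| 90% | 60% | 60% | 4.5% | 6.7% | 0.68 |
| 60% | 90% | 90% | 2.3% | 3.6% | 0.63 |
| 90% | 70% | 60% | 4.0% | 6.7% | 0.60 |
| 90% | 60% | 70% | 4.5% | 6.0% | 0.75 |

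**Step 4. A harsher assumption.** Suppose hypothermia is truly 5% in both arms (RR 1.00), non-cases consent at 80%, and consent among cases differs by arm. With 70% in UCM and 90% in ECC, the observed risks are 0.035/0.795 = 4.4% and 0.045/0.805 = 5.6%, RR 0.79. With the arms reversed, RR is 1.27.

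**The case against.** The total-cohort sentence is followed at once by the rule that infants stay in the arm to which they were assigned. It can be read as a rule about allocation, with missing outcomes left to the secondary-outcome paragraph, which does foresee a comparison by missingness and imputation. That reading softens the conflict. It does not remove it: the sentence covers all analyses, non-consent is nowhere named as a source of missing data, and the imputation has no trigger, model or list of variables.

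The numerical effect may also be minor. With consent equal by arm, the relative risk barely moves. The larger shifts need an assumed difference between arms. On the Step 3 rates, expected events are 600 × 0.0325 = 19.5 and 600 × 0.05 = 30, giving a 95% interval of about 0.37 to 1.14 around 0.65 even before clustering. A shift to 0.60 or 0.75 is small beside that. This stands, and it is why the point is a cheap improvement and not a fatal flaw.

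The waiver tier may also be less complete than it first appears. Families who opt out are excluded from it. The Abstract allows opting out after delivery, and Section VII seeks the full waiver for families the team could not reach. Whether minimal data are kept for parents who are approached and decline is unclear, so the documents do not support assuming waiver data on every infant. This stands and limits the remedy.

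**Conclusion.** The point holds for therapeutic hypothermia, volume expanders, hemoglobin, bilirubin and the ASQ-3/M-CHAT-R scores: the stated analysis population is not available for them. Selection by consent can bias these comparisons in either direction, by an amount the documents do not allow anyone to estimate. On the assumed rates the relative risk of 0.65 becomes about 0.63 to 0.68 with consent patterns equal by arm, and 0.60 or 0.75 with a 10-point arm difference among non-admitted infants.

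A reader might infer more than this:

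- **That the primary outcome is compromised.** It is not in the consent-only tier. Nor are death as a disposition or the resuscitation interventions.
- **That absolute risks will be overstated.** This follows only if admitted families consent more often. The second row of the Step 3 table gives risks that are too low.
- **That a complete-case result will be published as intention to treat.** No section makes complete-case the main analysis.
- **That HIE and race/ethnicity belong on the list.** Both are collected after consent, but HIE is exploratory and descriptive, and race/ethnicity is not an outcome.

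**What to change.** - In Section V, replace the blanket total-cohort statement with a named analysis set for each secondary outcome.
- Replace the open-ended imputation sentence with a prespecified analysis over all infants with waiver data: multiple imputation, or inverse-probability-of-consent weighting. Use gestational age, birth weight, tone, breathing, Apgars, resuscitation, NICU disposition, site, period and arm. Show the complete-case result beside it.
- Report numbers eligible, opted out, approached and consented, by arm and site-period.
- State whether minimal data are kept for parents who are approached and decline. If not, the adjusted analysis covers only infants with waiver data and must say so.

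Cost: plan wording and some extra analysis work, with no new data for infants already in the waiver tier. The downside is that the adjusted result relies on consent being explained by the waiver variables. Label: cheap improvement.
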